9. RESEARCH DESIGN AND METHODS

This is a randomized, 2-arm (1:1), double blinded clinical trial comparing pain scores at the time of osmotic dilator insertion and at specific points after insertion with a buprenorphine plus 1% lidocaine paracervical block compared to a paracervical block alone in women who have osmotic cervical dilators placed.

Primary Hypothesis:

In patients undergoing osmotic dilator insertion in preparation for dilation and evacuation, the addition of buprenorphine 0.15mg to a 1% lidocaine paracervical block will be associated with lower mean pain scores at time of osmotic dilator insertion compared to women who receive a 1% lidocaine paracervical block alone.

Secondary hypotheses:

In patients undergoing osmotic dilator insertion in preparation for dilation and evacuation, the addition of buprenorphine 0.15mg to a 1% lidocaine paracervical block will be associated with lower mean pain scores 2 hours after osmotic dilator insertion compared to women who receive a 1% lidocaine paracervical block alone.

In order to investigate this hypothesis, the following study design is proposed:

We plan to recruit at two study sites – the University of California, San Diego (UCSD) and Planned Parenthood of the Pacific Southwest (PPPSW). The UCSD study team will be responsible for all study procedures conducted at Planned Parenthood. Members of the UCSD study team will be determining eligibility, consenting patients, administering patient questionnaires, collecting data, and performing data analysis. Planned Parenthood clinicians will be administering the study medication during the procedure and will not be involved in any other research procedures.

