The primary outcome of the study is pain as measured on the NRS at the time of osmotic dilator insertion. Studies have varied in the time point at which pain is measured during the procedure, as some assessed pain with dilator insertion and others have recorded it 5 minutes after dilator insertion⁸⁻¹¹. Research studies addressing pain *during* osmotic dilator insertion have used the VAS, while studies looking at pain *after* dilator insertion have used the numeric rating scale (NRS)⁸⁻¹¹. We plan to capture pain using the NRS (an 11-point scale from 0-10) as we are evaluating pain at multiple different timepoints, both during and after dilator insertion.

Our secondary outcome is pain at 2 hours post dilator insertion. Given that buprenorphine can extend the length of analgesic effect by 2-3 times, we anticipate that the prolonged anesthetic effect should last anywhere from 2-6 hours using 1% lidocaine and provide pain relief as the dilators are expanding. Patients will be receiving text messages with links to questionnaires at three different time points (1 hour, 2 hours, and 6 hours post-insertion) in order to assess their level of pain, analgesic use, as well as any other symptoms. These text messages will be time stamped depending on time of dilator insertion and will be sent out at the intervals

	Before procedure	Paracervical block	Osmotic dilator placement (0 minutes)	5 minutes post dilator placement	1 hour post dilator placement	2 hours post dilator placement	6 hours post dilator placement	Prior to D&E
Baseline survey	x							
Pain scale	x	x	x	x	x	x	x	x
Side effect assessment			x	x	x	x	x	x
Clinician survey				x			x	
Assessment of oral analgesic medications needed					x	x	x	x
Participant satisfaction with pain control				x	x	x	x	x

we specify in the text messaging software.

Schedule of Assessments

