The table below indicates the time point at which the various assessments will be performed. Assessments will be performed over one to two days: on the day of osmotic dilator insertion and on the day of D&E. If same day dilators are used, the final assessment will be performed immediately prior to D&E. Overall, the process of clinician evaluation, procedural consent, study recruitment, study consent, performance of procedure, and immediate post-procedure questionnaire should take about 30 minutes. The follow up questionnaires and questionnaire prior to D&E will take about 10 minutes. Participants will receive a questionnaire sent via text message link at 1 hour, 2 hours, and 6 hours post-procedure. This questionnaire

assesses the need for oral analgesics for pain as well as participant satisfaction with their pain control at that study point. Participants will take a questionnaire on the morning of D&E asking them to rate their current pain and to recall their maximum pain score over the preceding day and their overall satisfaction with their pain control. The need for follow up will be determined per usual clinician practice and preference.

Randomization:

Block randomization will be performed in alternating blocks of 4 and 6 stratified by vaginal parity (vaginally nulliparous versus vaginally multiparous). The study team member will open the designated sealed sequentially numbered opaque randomization envelope containing computer generated randomization code of the type of paracervical block and hand it to the clinician performing the procedure. A clinician who will not be administering the paracervical block will then open the envelope and prepare the designated paracervical block into two 10 mL syringes. A different clinician blinded to the treatment group will perform the standardized procedure for osmotic dilator insertion using a speculum, 25-gauge spinal needle to inject the paracervical block, Dennison dilators to dilate the cervix if that is the clinician's practice, and insertion of laminaria and/or Dilapan-S. The amount of time it takes to inject the paracervical block will be recorded.

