It is suggested that a 2-point reduction in pain on the numeric rating scale (NRS) is clinically meaningful.²⁴⁻²⁷ No existing study parallels the outcomes of our proposed research (pain at time of osmotic dilator insertion using the numeric rating scale). One previous study used the Visual Analog Scale (a 0-100mm linear scale) to compare pain at the time of osmotic dilator insertion between a 1% lidocaine paracervical block and vaginal lidocaine gel.⁸ The visual analog scale and the numeric rating scale have modest correlation.⁴² The median pain score during osmotic dilator insertion in the 1% lidocaine paracervical block group was 61 (which correlates to 6 on the numeric rating scale) with a range from 0-100.

In order to detect a 2-point difference on the NRS at the time of osmotic dilator insertion with 80% power and a two-sided alpha of 0.05, we will need a total of 52 patients in each study arm (26 per arm). We plan to stratify the groups by vaginal parity (nulliparous versus multiparous) as vaginal parity may affect pain at the time of osmotic dilator insertion. In order to stratify by vaginal parity, we will need a total of 104 women (52 in each strata) to see a difference between strata per group. We plan to enroll an additional 10% to account for protocol deviation and participant dropout for a total of 114 participants. With a one to one randomization allocation, approximately half will be randomized to receive a paracervical block with buprenorphine and 1% lidocaine and half will receive a paracervical block with 1% lidocaine alone. Additionally, randomization will be stratified by vaginal parity (vaginally nulliparous versus vaginally multiparous).

Data Analysis

The baseline participant survey, NRS scores, side effects, and post-procedure participant and provider surveys will be performed by the study coordinator using REDCap loaded on to an electronic tablet. This data will be transferred to a spreadsheet in SPSS. Bivariate comparisons will be analyzed using chi squared test or Fisher’s Exact test for categorical variables and t-test or Mann-Whitney for continuous variables depending on the distribution of the data as appropriate. The primary outcomes will be evaluated per intent-to-treat analysis.

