16. PRIVACY AND CONFIDENTIALITY CONSIDERATIONS INCLUDING DATA ACCESS AND MANAGEMENT

Consent will be obtained in the patient's private exam room, in the private clinical space where participant can ask questions without feelings of embarrassment or discomfort. The physical exam will be conducted in the private examination room. Data will be reviewed by the principal investigator and research coordinators to ensure accuracy and completeness. Data will be monitored quarterly to ensure that data collection, coding, and management procedures are being conducted according to protocol and ethical guidelines.

There is a need for medical record access to assess patient demographics, history, and clinical outcomes. The baseline patient survey, NRS scores, side effects, and post-procedure participant and clinician surveys will be performed by the study team member using REDCap loaded on to an electronic tablet. REDCap is a secure, web-based application designed to support data capture for research studies, providing: 1) an intuitive interface for validated data entry; 2) audit trails for tracking data manipulation and export procedures; 3) automated export procedures for seamless data downloads to common statistical packages; and 4) procedures for importing data from external sources. Study data will be stored in the HIPPA-secure de-identified online REDCap data base housed at UCSD. Any printed study data will be secured in a locked cabinet/filebox, and only those directly involved in the study will have access to this including the investigators who will process it. Only de-identified data will be stored. Data entry and analysis will be performed on password-protected, institutionally secured computers. The research database will be banked indefinitely for the purpose of future research questions and will contain only de-identified information as above.

Participants will be contacted via text message to complete questionnaires at three different time points. The questionnaires will be sent over text via a hyperlink that connects to a secure platform that will input the data directly into a REDCap database. The application's template function will be used to ensure all outgoing text messages are uniform. Any incoming text messages are returned to the secure application platform. A key linking the participant's contact information to her participant ID will be stored in a locked cabinet in the study office separate from any data or patient information.

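### The text-collected 2-hour pain score has no missing-data plan and is compared by an unadjusted test, which can be biased if reply depends on earlier pain that differs by arm

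*Combined protocol and SAP*

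**What the plan says.** - **Status of the outcome.** Section 9 lists one secondary hypothesis, that the buprenorphine block "will be associated with lower mean pain scores 2 hours after osmotic dilator insertion", and later states "Our secondary outcome is pain at 2 hours post dilator insertion". Section 6 lists four secondary aims, and 2-hour pain is the first.
- **Collection.** Section 9 says "Patients will be receiving text messages with links to questionnaires at three different time points", and then gives the times: "Participants will receive a questionnaire sent via text message link at 1 hour, 2 hours, and 6 hours post-procedure". Section 16 adds that "The questionnaires will be sent over text via a hyperlink that connects to a secure platform". Neither section states a reminder, a call-back or a window within which a reply counts.
- **Earlier scores.** The schedule of assessments has pain rated before the procedure, at the block, at insertion and 5 minutes later, all before the first text. A study team member presents the scale at the block, at insertion and at 5 minutes. The 1-hour and 6-hour scores come by text, and pain is asked again before the D&E.
- **Analysis.** Data Analysis gives "t-test or Mann-Whitney for continuous variables depending on the distribution of the data as appropriate" for continuous variables. It states no missing-data rule, no repeated-measures model, and no adjustment for baseline pain or for vaginal parity, which stratifies randomization. Intention-to-treat is stated for the primary outcomes only.
- **Sample size.** The 10% allowance is for deviations and dropout in a calculation for the insertion score. No text-reply rate is assumed.

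**The concern.** The 2-hour comparison carries the claim that buprenorphine prolongs relief; Section 7 says pain after insertion under a lidocaine block peaks at that time. It depends on women answering a link with no staff present. A t-test or Mann-Whitney with no missing-data rule drops those who do not answer.

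Suppose women who hurt more in clinic reply less, and buprenorphine lowers pain in clinic. The control arm then loses more women, and more of its high-pain women. If earlier and 2-hour pain are correlated, the remaining controls look too comfortable and the arm difference shrinks. The scores that could correct this are already scheduled but have no role in the 2-hour comparison.

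**Working it through.** **The plan's own figure.** No sample size or reply rate is given for the 2-hour score. For the insertion score the plan needs 26 per arm for 2 points, 80% power and two-sided 0.05, but gives no SD. With an assumed SD of 2.5 (a quarter of the 0-10 range), n = 2 × (1.960 + 0.842)² × 2.5² / 2² = 24.5, so 25 per arm by the normal formula and 26 by the t-test. An SD of 2.5 is therefore consistent with the plan. The total follows as 104 × 1.10 = 114.4, stated as 114.

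**Why two conditions are needed.** Let b be the log-odds of non-reply per NRS point of earlier pain, σ the SD, ρ the correlation of earlier with 2-hour pain, and p the non-reply proportion in an arm. For small b, the mean earlier score among responders shifts by about −bσ²p, and the 2-hour mean by ρ times that. With the same b in both arms, the shrinkage of the arm difference is about

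ρ × b × σ² × (p control − p buprenorphine).

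If earlier pain is equal in the arms, the two p are equal and the result is zero.

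**Numbers, 57 per arm (114/2), true 2-hour difference 2.** All drivers are assumed; 1,500 simulated trials per scenario.

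- No earlier effect: responders-only estimate 1.98-2.02, so no bias.
- Earlier effect 2 points, ρ = 0.7, b = 0.3 (odds ×1.35), non-reply 35.6% control and 24.5% buprenorphine: the formula gives 0.7 × 0.3 × 6.25 × 0.111 = 0.15. Simulation gives 1.88, a shrinkage of 0.12.
- The same with 12.4% and 7.4%: formula 0.7 × 0.3 × 6.25 × 0.050 = 0.07; simulation 1.94, a shrinkage of 0.06.
- Steepest case, b = 0.6 (odds ×1.82), 39.2% and 21.4%: simulation 1.66, a shrinkage of 0.34 (the formula overstates when b is large). Power is 86.1%, against 95.7% when the earlier score is used.
- Across ρ = 0.3-0.7 with an earlier effect of 2 points, the estimator using the earlier score gives 1.96-2.01.
- Earlier effect 2 but no true 2-hour effect, b = 0.6: a false difference against buprenorphine of 0.08-0.14 at 10% non-reply (type I error about 6%) and 0.14-0.36 at 30% (6-10%).

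**Numbers, 52 per arm (104/2), true difference 1.5.** Assumed: SD 2.5, correlation 0.4-0.6, about 15-40% non-reply, b = 0.3-0.5.

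- No in-clinic effect, same reply rule: responders-only 1.48-1.53, so no bias.
- In-clinic effect 1-2 points, same rule: responders-only about 1.24-1.46, which is 0.04-0.26 points or 3-17% too small (0.04/1.5 to 0.26/1.5). Using the in-clinic scores gives about 1.5.
- No in-clinic effect, pain-reply link in one arm only (b = 0.5): responders-only 0.91-1.32, against 1.48-1.52 using the in-clinic scores. This is the direction when the link is in the control arm. In the buprenorphine arm it inflates the difference by the same amount: 1.5 + (1.5 − 1.32) = 1.68 to 1.5 + (1.5 − 0.91) = 2.09.
- The standard error is about 0-10% smaller with the earlier scores.

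**Direction.** One might expect the sign to flip if women in more pain reply more. Under a common logistic rule it does not: b turns negative, but the arm with more non-reply also switches. In the second example above, 0.7 × (−0.3) × 6.25 × (0.245 − 0.356) = +0.15, the same shrinkage. A simulation run to check this agreed. The sign can change when the link differs by arm.

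**The case against.** Four points on the other side have force.

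- **Bias is not automatic.** A reader might infer that pain-related non-response by itself biases the result. It does not: under one reply rule, with equal earlier pain in the arms, the responders-only estimate is unbiased. This stands.
- **The scores are not unused.** A reader might infer that the repeated scores go to waste. Section 9 chose the scale "as we are evaluating pain at multiple different timepoints, both during and after dilator insertion", and the outcomes list makes these scores outcomes in their own right. They are unused only as information for the 2-hour comparison. Nor does the plan write down a responders-only analysis; that is what the named tests do when nothing else is said.
- **The size is modest.** A shrinkage of 0.04-0.26 points compares with a standard error of roughly 0.5-0.6 and the plan's 2-point meaningful difference. Random non-reply costs little: with 57 per arm randomized and SD 2.5, power for 2 points is 98.9% at full reply and 94.2% at 70% reply. Reply rate, SD, correlation and reply slope are all assumptions.
- **A mixed model is not a full cure.** If reply depends on the unseen 2-hour pain itself, neither analysis is protected. The simulations also tested regression on complete earlier scores, not a five-time model in which the 1-hour and 6-hour texts may be missing too.

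These points limit the claim but do not remove the gap. The condition that creates bias under a common reply rule, lower in-clinic pain on buprenorphine, is what the trial sets out to show. Section 14 lists sleepiness and dizziness among the drug's side effects, so reply behaviour that differs by arm is plausible, though not shown.

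**Conclusion.** The concern holds in conditional form. The only listed secondary hypothesis rests on a text-collected score with no missing-data plan and an unadjusted test that by default uses responders only. Bias arises if reply depends on earlier pain that differs by arm, or if the pain-reply link differs by arm. With a common reply rule and in-clinic effects of 1-2 points, a true 1.5 becomes about 1.24-1.46 under the assumed inputs. If the link exists in one arm only, the error can be larger and can go either way.

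The documents do not support saying that the 2-hour result will be biased, or that replies will be poor; no reply rate is given. The primary outcome, scored in clinic, is not affected.

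**What to change.** In Data Analysis, prespecify for the 2-hour outcome:

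1. A mixed model for repeated measures on NRS from insertion through 6 hours, with arm, time, arm-by-time, baseline NRS and vaginal parity, an unstructured covariance and all available scores from every randomized woman. Equivalent multiple imputation using the in-clinic scores and parity would also serve. Scores taken after randomization should enter as outcomes or imputation variables, not as covariates in a responders-only test.
2. The 2-hour arm difference with its 95% CI as the secondary result. This is a difference in means, as the hypothesis is worded.
3. Reply rates by arm at 1, 2 and 6 hours.
4. The responders-only test as a sensitivity analysis.
5. A missing-not-at-random sensitivity analysis that shifts the missing 2-hour scores by a range of deltas, separately by arm.

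Stating a reply window and reminders would also help limit missing scores. Section 9 should be reconciled as well: one paragraph says the text questionnaire covers pain level, while another describes it as covering analgesic need and satisfaction only.

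The cost is one paragraph and a little more analysis work, with no new data. The downside is that the main model assumes missingness depends only on observed scores, which is why item 5 is needed.

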Included in the study are women who present to the UCSD or PPPSW clinics seeking dilation and evacuation for any indication and who will require cervical preparation with osmotic dilators as determined by the evaluating clinician. Patients between 14 weeks 0 days gestation to 23 weeks 6 days gestation at the time of osmotic dilator insertion will be candidates for study inclusion. Participants will be excluded based on a brief questionnaire if they have a known allergy to the study medication or ibuprofen, any chronic pain conditions, have taken any narcotic medications in the last 24 hours, have chronic opiate use or any other drug abuse, request sedation during laminaria insertion, or have a history of chronic liver disease. Stratified randomization will be performed among participants based on vaginal parity (nulliparous and multiparous). Participants will be randomized to one of two study groups allocated one to one: (1) paracervical block with 20mL of 1% buffered lidocaine or (2) paracervical block with 20mL of 1% buffered lidocaine plus 0.15mg of buprenorphine.

During the procedure, the study team member will present the numeric rating scale (NRS) to the participant and ask her to mark her level of pain at each time point during the procedure (paracervical block placement, osmotic dilator insertion, 5 minutes post procedure) and will remain blinded to the study arm. These NRS scores will be recorded into REDCap utilizing an electronic tablet. The participant will be asked

about side effects such as dizziness and nausea during the procedure. The clinician will perform the osmotic dilator insertion in the usual fashion, and the study team member will record the time from speculum insertion to speculum removal.

After the procedure, the clinician will answer a brief questionnaire detailing if there were any adverse events or difficulty related to either the paracervical block or the osmotic dilator insertion. The clinician will also note whether or not cervical dilation was performed prior to osmotic dilator insertion and to what size dilator. They will also indicate their level of training. At 5 minutes after osmotic dilator insertion, the participant will indicate her level of pain and answer questions regarding side effects and satisfaction with pain control during the procedure.

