11. RECRUITMENT

The study will take place at UCSD and Planned Parenthood of the Pacific Southwest. Patients either self-refer to these clinics or are referred by another clinician. At UCSD, appointments are coordinated by a Family Planning Manager. During the time of the study, when a participant presents to clinical care for a D&E for any indication, she will be counseled on options including induction termination and D&E. If the patient desires a D&E and is at PPPSW, she will be assessed for ability to perform this procedure in the outpatient surgical center. If the patient has medical co-morbidities that increase the risk of the procedure, she may be referred to UCSD or another tertiary care center.

If the patient is a good candidate for D&E and the procedure is scheduled to occur the next day, the clinician will assess the need for osmotic dilator placement for cervical preparation; this is usually known based on gestational age, however patients between 14 weeks to 16 weeks may receive either dilators or misoprostol alone. This will be determined per clinician judgement. If the patient is eligible for osmotic dilator placement, informed consent will be obtained for the procedure, per standard clinic practice, and the clinician will notify the study team member. The study team member will then assess if the patient is interested in participating in the study, ensure that the patient is willing to be randomized to the study medication, and assess whether or not she has already taken ibuprofen that day in preparation for osmotic dilator placement. Eligibility criteria will be verified by the study team member using the script below. The study team member will obtain written informed consent to participate and perform the baseline survey. The participant will receive 800mg of oral ibuprofen if she has not already taken this medication prior to the appointment.

We will use the below recruitment script:

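### Fixed alternating block sizes make some upcoming allocations certain to anyone who has read the earlier codes; computer-chosen random sizes would remove most of that certainty at almost no cost

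*Combined protocol and SAP*

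**What the plan says.** All of the following is in the combined protocol and SAP.

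- **Block structure.** Section 9, Randomization: "Block randomization will be performed in alternating blocks of 4 and 6 stratified by vaginal parity". The text does not say which size comes first, whether each site has its own list, or whether the sizes are withheld from staff. Allocation is 1:1.
- **Who reads the code.** The same paragraph says: "A clinician who will not be administering the paracervical block will then open the envelope and prepare the designated paracervical block". A different clinician, described as blinded, then injects the block and inserts the dilators. This separation is stated for each participant. There is no rule about who may act for the next one.
- **Who handles the envelope.** Just before that: "The study team member will open the designated sealed sequentially numbered opaque randomization envelope". That person then passes it to the clinician performing the procedure. Earlier in Section 9, the study team member who collects the pain scores is said to stay blinded.
- **Who decides on dilators.** Section 9 includes women "who will require cervical preparation with osmotic dilators as determined by the evaluating clinician", and Section 10 repeats this as a matter of clinician judgement. Section 11 names one range where the choice is open: "patients between 14 weeks to 16 weeks may receive either dilators or misoprostol alone".
- **Limits on clinicians.** Section 9 gives eligibility and consent to the UCSD study team. It says that Planned Parenthood clinicians give the study medication and take no part in other research procedures.

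**The concern.** Varying the block size helps because an observer who has followed the sequence cannot tell where a block ends. If the sizes alternate in a fixed order that is printed in the protocol, that uncertainty is largely gone. Once one arm is used up within a block, every remaining allocation in that block is determined. Sealed opaque envelopes do not help, because the inference comes from codes already read.

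The main route to harm is the operator. A clinician who prepared earlier syringes in a stratum and later acts as the blinded operator could know the arm. The primary outcome is a self-reported 0–10 pain score during insertion. The way the operator injects, dilates (left to the clinician's practice) and talks to the patient could affect it.

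A minor route is enrolment: a clinician expecting a particular arm could be influenced in choosing between dilators and misoprostol alone. The documents describe that choice as open only at 14 to 16 weeks.

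**Working it through.** The plan gives no figure for predictability, so there is none to reproduce. The quantity computed is the share of allocations that an observer knows for certain before the envelope is opened.

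**Inputs.** Block sizes 4 and 6, alternating within stratum, 1:1 allocation, two parity strata (Section 9). Planned enrolment is 114 (Section 9, Power Calculation), taken here as 114 / 2 = 57 per stratum. The equal split is an assumption.

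**Certain allocations per block.** In a 1:1 block of size 2m, the next allocation is certain once one arm has been used m times. The expected number of certain allocations is 2m/(m + 1).

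- Size 4 (m = 2): 4/3 = 1.33. Check: of the 6 orderings, 2 end in a run of two and 4 in a run of one, so (2×2 + 4×1)/6 = 1.33.
- Size 6 (m = 3): 6/4 = 1.50. Check: of the 20 orderings, 2 end in a run of three, 6 in a run of two and 12 in a run of one, so (6 + 12 + 12)/20 = 1.50.
- Per pair of blocks: (1.33 + 1.50)/10 = 28.3%.

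**Over 57 per stratum, starting with a block of 4.** Five complete pairs, one block of 4, and the first three places of a block of 6 (where nothing can yet be certain): 5 × 2.833 + 1.333 + 0 = 15.5. Then 15.5/57 = 27.2%, or 31 of 114 over both strata.

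**Weaker knowledge, and the alternative design.** These come from simulated lists of 57 per stratum. The observer rules out every sequence inconsistent with what has been seen. In the partial-knowledge rows, the seen codes are a random share of the earlier ones.

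| Earlier codes seen in the stratum | Fixed alternation | Sizes 4 or 6 at random |
|---|---|---|
| All, first size known | 27.2% | 5.4–5.6% |
| All, first size unknown | 23.2% | – |
| 75% | 13–14% | 1.4% |
| 50% | 5.2% | 0.3% |

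The upper end of the 75% row under alternation (13.9%) comes from counting complete pairs of blocks instead of stopping at 57. If only 25% of codes are seen, the alternating figure is about 1%.

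**Best-guess accuracy.** An observer with full knowledge who always guesses the more likely arm is right about 69% of the time under either scheme (68.8% alternating, 68.8–68.9% random order). The best guess is simply the arm that is behind in the current block, and randomising the sizes hardly changes that.

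**Imbalance.** If enrolment stops mid-block, the largest possible difference between arms in a stratum is half the largest block: 6/2 = 3 under both schemes.

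**Envelope handling, side by side.** One sentence has the study team member open the envelope and give it to the clinician performing the procedure. The next has a clinician who is not giving the block open it. The one after calls the operator blinded, and an earlier paragraph of Section 9 keeps the study team member blinded. Read literally, these cannot all hold.

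**The case against.** The strongest case against the point is that it rests on staffing the documents do not describe. No section says that the same clinicians take turns preparing, evaluating and operating. At Planned Parenthood, clinicians are confined to giving the study medication. If opening an envelope and preparing a study block counts as a research procedure, operators there never see a code. One list shared across both sites would also make the sequence harder to follow. All of this stands, and it is why 27% is an upper bound. It does not dispose of the point: the limit is written for Planned Parenthood only, and nothing bars a UCSD preparer from operating later.

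The enrolment route is thin. Section 11 says the need for dilators is usually known from gestational age. The UCSD team verifies eligibility and obtains consent, and both arms receive the standard lidocaine block (Section 13 names it as standard care), so there is no obvious motive to steer. This also stands. A reader might infer that clinicians can choose whom to enrol by arm. The documents support at most a narrow opening at 14 to 16 weeks, and give no share of patients in that range.

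Finally, the fix leaves best-guess accuracy where it was. That is correct. The gain is limited to certain knowledge, which is the most direct threat to a blinded operator but not the only one.

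**Conclusion.** The point holds as an avoidable weakness in the randomization, not as evidence of bias. With full knowledge of earlier codes in a stratum, alternation makes up to about 27% of allocations certain (about 23% if the first size is unknown), against 5–6% with randomly ordered sizes. The figure drops quickly as fewer codes are seen. It assumes an observer who tracks positions within the stratum and, for the full figure, has seen every earlier code there.

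Two stronger readings should be avoided. A reader might infer that about 31 of 114 allocations will in practice be known to operators. That would need complete knowledge of both strata across both sites, plus a rotation of roles that the documents do not state. A reader might also infer that random block sizes would make the sequence unpredictable. They would not, since best guesses remain about 69% correct.

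The contradiction over the envelope is a separate matter. It concerns the current participant's arm, needs no inference from past codes, and is not cured by changing the block sizes.

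**What to change.** 1. In Section 9, Randomization, replace the alternating order with permuted blocks whose sizes (4 or 6) are chosen at random by computer within each parity stratum.
2. Keep the block sizes in a document that clinic staff and the study team member at the bedside do not receive.
3. State beside the change that it removes most certain knowledge of upcoming arms but leaves best-guess accuracy at about 69%.
4. Reconcile the statements in Section 9 on who opens the envelope, who receives it and who remains blinded, so that one consistent sequence is written down.

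Made before enrolment, the cost is one changed sentence, a regenerated allocation list and envelope set, and a short clarification of envelope handling. No patients or study procedures are added, and the maximum mid-block imbalance stays at 3 per stratum.
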